6.2.4 Clinical Laboratory Evaluations

Urine samples will be collected and blood will be drawn from each subject at screening and on Day 3, and Day 8, as presented in [Table 1](#). The clinical laboratory parameters evaluated in this study are presented in [Table 3](#).

Clinical laboratory tests will be reviewed for results of potential clinical significance throughout the study. The Investigator will evaluate any change in laboratory values. If the Investigator determines a laboratory abnormality to be clinically significant, the abnormality will be reported as an AE (see [Section 6.2.1](#) for definition of clinically significant laboratory results). Clinically significant laboratory results will be followed up to resolution or until the Investigator considers the abnormality chronic and/or the subject to be stable.

Urine pregnancy testing and all laboratory assessments will be done by a local laboratory.

Table 3 Clinical Laboratory Tests

[figure not shown]

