5.1 General Analysis Considerations

The statistical analysis will be performed using [REDACTED]. Any deviations from the planned analysis as described in this SAP will be justified and recorded in the CSR.

The data documented and the clinical parameters measured in this study will be described using descriptive statistics (including number [n], mean, median, Standard Deviation (SD), minimum, and maximum) for continuous variables: minimum and maximum will be presented to the same number of decimal places as the raw data, mean and median will be presented to one more decimal place than the raw data, and SD will be presented to two more decimal places than the raw data. If the geometric mean is to be presented, it will be set to the same precision as the mean. However, geometric mean will not be calculated when minimum value from the data is zero. Percent Coefficient of Variation (CV%) will be presented to two decimal places. P-values will be rounded to three decimal places. If a p-value is less than 0.001 it will be reported as "<0.001". If a p-value is greater than 0.999 it will be reported as ">0.999".

Categorical data will be summarized using count and percentage in each category. Percentages will be presented to one decimal place. The percentage will be suppressed when the count is zero in order to draw attention to the non-zero counts. "Not done" and "Missing" category will be included to account for cases of no assessment and missing respectively even if they are not recorded in eCRF. The denominator for all percentages will be the number of subjects within the treatment group for the population of interest, unless otherwise indicated.

All data will be displayed in listings. Unless otherwise specified, listings will be sorted by the treatment group, subject number, and assessment date or visit date, if applicable. In cases where more ordering is required, other variables will be included in the sort order as applicable.

Baseline will be the latest available measurement prior to the start of the infusion of study drug.

When summarizing End-of-Study (EOS) visit, the early termination cases are excluded from the summary for EOS visit, but will be presented in data listings. Unscheduled results will not be included in the summary tables except for determining baseline or if unscheduled results are necessary to interpret data, but they will be presented in data listings.

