12.2 Clinical Laboratory Analyses

Clinical laboratory (hematology, biochemistry, urinalysis) tests will be performed in local laboratories and results will be converted to standard units that are defined as in the sections 12.2.1, and 12.2.2.

Hematology, biochemistry and urinalysis parameters will be labeled with a CTCAE term and grading will be applied to post-baseline values for the parameters where possible according to CTCAE v 4.03. When CTCAE grade is upon clinical input only, the grading will not be applied, but grade require numeric and partial clinical input, grade will be assigned based on the numeric portion only. The CTCAE terms and grades for applicable parameters are listed in [Appendix 14.2.1](#). The CTCAE grades for this analysis will be Grade 1 (Mild), Grade 2 (Moderate), Grade 3 (Severe) and Grade 4 (Life-threatening). The CTCAE Grade 5 (Death) will not be applied in this analysis since death cannot be determined from a numeric laboratory result. If the post-baseline result for a subject does not satisfy any CTCAE grade, it will be classified as "No Grade". If a laboratory parameter value falls within the local normal range, the grade will be classified as "No grade" even if the value has the numeric grade according to CTCAE v 4.03.

If the laboratory parameter value falls in outside the normal range: 'low' or 'high', they will be flagged in each visit. All hematology, biochemistry and numeric urinalysis data will be listed with high and low flags to show if a value is outside the normal range.

The results for all hematology, biochemistry and categorical urinalysis parameters will be categorized into Normal, Abnormal/Not Clinically Significant (NCS) or Abnormal/Clinically Significant (CS) using the local laboratory normal ranges used by study site and provided by local laboratory prior to analysis.

The number and percentage of subjects with a result for each grade will be summarized by CTCAE term, CTCAE grade and actual treatment group. The summary includes only the most severe case during the overall visits.

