12.2.1 Hematology

The following hematology laboratory tests will be included: White blood cells (WBC) ($10^9/L$), Red blood cells (RBC) ($10^{12}/L$), Hemoglobin (g/dL), Hematocrit (Proportion of 1.0), Platelet ($10^9/L$), Neutrophil (Proportion of 1.0), Lymphocyte (Proportion of 1.0), Monocyte (Proportion of 1.0), Eosinophil (Proportion of 1.0), Basophil (Proportion of 1.0), Absolute Neutrophil Count (ANC) ($10^9/L$). In addition, Absolute Lymphocyte Count (ALC) ($10^9/L$) will be calculated as follows: $[WBC (10^9/L) * Lymphocytes (Proportion of 1.0)]$. It will be presented in the listing with CTCAE grading and summarized in the CTCAE grading table, but will not be included in the hematology summary tables.

Statistical Analysis Plan

All hematology parameters will be summarized by parameter and actual treatment group for all scheduled collection times (Baseline, Day 3, Day 8) using descriptive statistics. Also, the additional shift table regarding the results of normality (Normal, Abnormal/NCS, and Abnormal/CS) will be summarized for all scheduled collection visit. All hematology test result data will be listed for each subject by actual treatment group, visit and individual test results.

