12.8 Chest X-ray

Chest X-ray assessment will be performed at screening. If symptoms have not relieved up to Day 3, chest X-ray will be performed to determine presence of secondary complications of influenza A infection. Moreover, if the investigator considers chest X-ray is necessary, then it will be performed during the study to evaluate the lower respiratory tract. Findings will be classified as "Normal", "Abnormal, NCS" or "Abnormal, CS". The number and percentage of subjects regarding the result of chest X-ray assessment will be summarized by actual treatment group and visit in the form of a shift table to detect changes from baseline.

All chest X-ray result will be listed for each subject by actual treatment group and visit.

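### By default SAP 5.1 leaves unscheduled results out of the worst-grade laboratory table and discretionary films out of the chest X-ray shift table, and no safety section says otherwise

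*SAP*

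**What the plan says.** **General rule.** SAP 5.1 says: "Unscheduled results will not be included in the summary tables except for determining baseline or if unscheduled results are necessary to interpret data". The sentence goes on to say of these results, "but they will be presented in data listings". The same paragraph says of the end-of-study summary that "the early termination cases are excluded from the summary for EOS visit".

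**Laboratory.** SAP 12.2 says CTCAE "grading will be applied to post-baseline values for the parameters where possible", and of the grade table: "The summary includes only the most severe case during the overall visits". The descriptive tables in SAP 12.2.1 are expressly limited: "for all scheduled collection times (Baseline, Day 3, Day 8) using descriptive statistics". Protocol 6.2.4 says: "Clinically significant laboratory results will be followed up to resolution", or until the investigator regards the abnormality as chronic or the subject as stable.

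**Chest X-ray.** The schedule of assessments has a screening film and a conditional film at Day 3 for subjects whose symptoms have not been relieved. SAP 12.8 adds that "if the investigator considers chest X-ray is necessary, then it will be performed during the study". The results go into a shift table by treatment group and visit.

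**The concern.** Leaving unscheduled values out of a by-visit table of means is ordinary practice. A table of each subject's worst value has a different purpose: it should find the peak wherever it occurred. Tests outside the schedule are often done because something already looked abnormal, so they are a likely place for the peak to appear. If SAP 5.1 is applied as a blanket default, the worst-grade table becomes the worse of two planned draws, and a late chest film has no line in the table meant to show change from baseline.

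At stake are the per-arm counts of graded laboratory abnormalities and of new abnormal chest films. In a dose-ranging study with about 70 subjects per active arm, counts of severe grades may be small enough for one subject to matter. The exception in 5.1 adds a second problem. It names no criterion, no decision-maker, no deadline and no table, so whether a given unscheduled result is tabulated is left open.

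**Working it through.** The plan states no figure on this point, so there is nothing to reproduce. The check compares the sections and then does simple arithmetic for scale.

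**1. Does any section lift the default?** SAP 10.2 does so for efficacy: it says that unscheduled site temperatures join the scheduled ones in the secondary time-to-event analyses. SAP 12.2 (laboratory) and 12.8 (chest X-ray) contain no such statement. A programmer following the text would apply 5.1 to both.

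**2. Will unscheduled laboratory values exist?** Scheduled draws are at screening, Day 3 and Day 8 (Protocol Table 1 and 6.2.4). Follow-up runs to Day 110. After Day 8 there are 110 − 8 = 102 days, and 102 / 110 = 92.7% of follow-up, in which any laboratory value is by definition unscheduled. A clinically significant Day 8 result that is followed as Protocol 6.2.4 requires therefore produces unscheduled values.

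**3. What would the grade table show?** The SAP 14.2.1 grading of ALT illustrates it. Above 3.0 and up to 5.0 times the upper limit of normal is Grade 2, and above 5.0 up to 20.0 times is Grade 3. Take a subject in the Grade 2 band on Day 8 whose follow-up test falls in the Grade 3 band.
- Under the 5.1 default, Table 14.3.4.1 counts the subject as Grade 2.
- If SAP 12.2's reference to post-baseline values is taken at face value, the table counts Grade 3.

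The text supports both readings and does not rank them.

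**4. Chest X-ray.** The Day 3 film is a conditional entry in the schedule, so it is scheduled and has a visit row. Investigator-requested films at other times have no scheduled visit and therefore no row in Table 14.3.5.8.

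**5. Is the adverse-event route equivalent?**
- Under SAP 12.1.1 only clinically significant laboratory results count as TEAEs. A numerically high grade judged not clinically significant does not enter that way.
- Under Protocol 6.2.1.5 the diagnosis, or else the signs and symptoms, is entered in place of the laboratory finding where either is available.
- SAP 12.2 grades on the numeric part of the criteria only, whereas AE intensity is the investigator's assessment.

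The TEAE tables therefore do not reproduce the numeric grades.

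**6. Who could exercise the exception?** The first report includes second-season data only to Day 15, with later data held for the follow-up report (SAP 1.1). Protocol 5.8.1 has the sponsor and relevant CRO biostatisticians unblinded for reporting. Without a prior rule, the decision about later unscheduled results could be taken with knowledge of allocation.

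**7. Scale.** The planned arms are 70, 70 and 43 subjects (SAP 1.1).
- One missed subject: 1 / 70 = 1.4 percentage points in a CT-P27 arm, and 1 / 43 = 2.3 points on placebo.
- Let p be the proportion of subjects whose worst value is unscheduled. The documents give no p, so the values below are assumptions. The chance of at least one such subject in an arm of n is 1 − (1 − p)^n.

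| Assumed p | Expected, n = 70 | At least one, n = 70 | Expected, n = 43 | At least one, n = 43 |
|---|---|---|---|---|
| 1% | 0.7 | 51% | 0.43 | 35% |
| 2% | 1.4 | 76% | 0.86 | 58% |
| 5% | 3.5 | 97% | 2.15 | 89% |

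**The case against.** The strongest reply is that nothing is hidden and the laboratory exclusion is not certain. Unscheduled results are listed. The exception in 5.1 permits their inclusion when they are needed. SAP 12.2.1 uses the word scheduled for the descriptive tables, while 12.2 does not use it for the grade table, so the specific section may fairly be read as prevailing. Clinically significant laboratory abnormalities become TEAEs, a recurring event takes its most severe grade (Protocol 6.2.1.4), and Table 14.3.1.5 isolates Grade 3 and above. Complications seen on a film are reported as adverse events and tabulated (Protocol 6.1.5, SAP 10.2). All arms share one schedule, and no bias between arms has been shown.

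Most of this stands as a limit on the point. It rules out saying that these results are certainly omitted or that the signal disappears from the report. It does not remove the conflict between 5.1 and 12.2. Nor does it make the TEAE tables a substitute for numeric grades, and listings give no counts by arm.

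A reader might infer more: that all tests prompted by a problem, including ECGs and the symptom-triggered film, drop out of the tables. The documents do not support that.
- The Day 3 film is a conditional scheduled assessment and stays in.
- The repeat ECG in Protocol 6.2.8 follows an ECG already judged clinically significant. If that ECG was a scheduled one, the subject already sits in the top category of the SAP 12.5 shift table, and a repeat cannot show a worse one.

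**Conclusion.** The point holds in a limited form. As a default, not a certainty, SAP 5.1 keeps unscheduled values out of the worst-grade laboratory table, and 12.2 does not resolve the matter. Discretionary chest films outside Day 3 have no place in the by-visit shift table. Any resulting error is an understatement of those counts.

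Its size cannot be established from the documents. The per-subject steps and the assumed range above show only that a single case is plausible and would be visible in arms of this size. The conclusion assumes that 5.1 is applied as written wherever a safety section is silent, and that some subjects have an off-schedule result worse than their scheduled ones. The loss concerns graded and shift-table counts, not all safety reporting. The change is cheap and worth making.

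**What to change.** - **SAP 12.2:** state, as an exception to 5.1, that Table 14.3.4.1 uses all post-baseline results, whether scheduled, unscheduled or from early termination.
- **SAP 12.8:** add a worst post-baseline row, including unscheduled films, to Table 14.3.5.8.
- **By-visit descriptive tables:** leave them restricted to scheduled visits.
- **SAP 5.1:** define the interpretive exception before unblinding, giving the criterion, who decides and which tables it affects. Defining it is better than deleting it, because it is the only general clause that admits needed unscheduled results after baseline.

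The cost is a few sentences and minor programming, with no new data collection. Reported abnormality rates may be slightly higher.

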5.2 Determination of Sample Size

This study is designed to obtain effect sizes of 2 different CT-P27 treatment groups and placebo group based on the time from the administration of study drug to resolution of influenza symptoms and fever.

For this proof-of-concept dose-ranging study, assuming 90% of subjects are included in the eligible infected population, the total eligible sample size of 164 (63 eligible infected subjects per CT-P27 treatment groups and 38 subjects in placebo group) achieves 80% power to detect 1.8 days of reduction for the primary endpoint of time to resolution with 5% two-sided significance level and SD of 3 days using a Wilcoxon's rank-sum test.

Considering a dropout rate of 10%, this study will need 183 subjects to be enrolled to achieve 164 evaluable subjects.

For an effect size of 1.5 days of reduction in time to resolution with SD of 2.9 days, the total sample size could be increased to about 250 to achieve at least 80% statistical power with 5% two-sided significance level.

5.3 Analysis Populations

ITT and ITTI populations will be analyzed according to the randomized treatment groups and safety and PK populations will be analyzed according to the actual treatment groups.

- Intent-to-Treat (ITT) Population: defined as all subjects randomized to study drug. All subjects will be included in the ITT as randomized even if they do not receive treatment, except

Statistical Analysis Plan

for the following situation:

Subjects who are screening failures but are randomized in the IWRS by accident and do not receive any study drug will not be included in the ITT population.

- Intent-to-Treat Infected (ITTI) Population: defined as all randomized subjects with confirmed influenza A by quantitative Polymerase Chain Reaction (qPCR) or cell culture.
- Safety Population: defined as all randomized subjects receiving any amount (full or partial dose) of study drug, except for the following situation:
Subjects who do not receive study drug but receive normal saline solution will be included in the safety population and they will be analyzed in the placebo group.
- PK Population: defined as all randomized subjects with confirmed influenza A by qPCR or cell culture who received a complete dose of study drug, with at least one post-dose PK sample.

If infusion interruptions and/or infusion rate adjustments occur during the drug administration, the subject is still considered to have received a complete dose provided that the full calculated dose (45 mg/kg or 90 mg/kg) has been given at the end of the infusion.

The analysis populations will be used for the analyses as follows:

- ITT Population:
 - Demographic and baseline characteristics
 - Use of drugs for symptom relief
 - Secondary efficacy endpoints
- ITTI Population:
 - Demographic and baseline characteristics
 - Primary efficacy endpoint
 - Secondary efficacy endpoints
 - Genotype
 - Phenotype
- Safety Population:
 - Viral serology
 - Prior and concomitant medications
 - Study drug exposure
 - Safety endpoints
 - Immunogenicity
- PK Population:
 - Demographic and baseline characteristics
 - PK analysis
 - HI antibody

HI antibody, genotype and phenotype will be analyzed in the Follow-Up CSR only.

5.4 External Data Handling

When combining data from eCRF and that of analytical facilities such as [REDACTED], discrepancy will be handled as follows:

- 1) Recorded as collecting sample in eCRF but no corresponding results from analytical facility – listing will display only sample collection visit/date/time from eCRF;
- 2) No corresponding records in eCRF for results from analytical facility – listing will display only specimen collection visit/date and results from analytical facility;
- 3) Discrepancy in sample collection date from eCRF and analytical facility – listing will display results from analytical facility and visit/date/time from eCRF if not missing; if sample collection date/time is missing in

CONFIDENTIAL

Statistical Analysis Plan

eCRF then use specimen collection visit/date from analytical facility.

6. Protocol Deviation

Subject data will be reviewed for major protocol deviations by a qualified clinical reviewer prior to the blinded Data Review Meeting (DRM). In the DRM, all analysis populations will be also reviewed and documented prior to unblinding the study. The protocol deviations will be classified as 7 types:

- Inclusion/Exclusion criteria & Consent procedure
- Investigational Product (IP) dosing error, IP usage error
- IP dispensing error
- Use of unauthorized treatment (e.g., prohibited drug, restricted drug)
- Visit window deviation
- Failure to perform required study procedure
- Other

Protocol deviation listing with classified type and description of deviation will be presented for the ITT population.

7. Subject Disposition

The number of subjects who are screened, randomized, and treated with study drug will be summarized in the ITT population. Reason of screening failure will be summarized overall and the number of administered subjects who have completed or discontinued study will be summarized with reason of discontinuation by treatment group and overall.

A subject will be considered to have been randomized if the subject is allocated to a randomization number as recorded on the 'Randomization Requirements' page of the eCRF. A subject will be considered to have administered treatment in the study if "Yes" was recorded for the question, 'Was the Study Drug Administration performed?' in 'Study Drug Administration' page of the eCRF. A subject will be considered to have completed the study if "Yes" was recorded for the question, 'Did the subject complete the study?' in 'End of Study' page of the eCRF. Likewise, a subject is considered to have discontinued the study if "No" was recorded for the same question. A subject will be considered to be ongoing the study if they have been randomized and no information has been yet recorded in the 'End of Study' page of the eCRF.

8. Demographics and Baseline Characteristics

Demographics and other baseline characteristics recorded at screening visit will be presented in summary tables and listings for populations of interest.

8.1 Demographics and Subject Characteristics

The following continuous variables will be summarized using descriptive statistics by treatment group:

- Age (years)
- Height (cm)
- Weight (kg)
- Body Mass Index, BMI (kg/m²)

Age will be automatically calculated in the eCRF system based on the date of the informed consent visit and the year of birth considering whether birth date has passed the informed consent date or not. BMI will be automatically calculated in the eCRF system as: $\text{Weight (kg)} / [\text{Height (m)}]^2$ using weight and height from 'Weight' and 'Subject Characteristics' pages of the eCRF.

The following categorical variables will be summarized in contingency tables:

- Sex (Male, Female)
- Fertility status (if female – Childbearing potential, Sterility, Menopause)

CONFIDENTIAL

Statistical Analysis Plan

- Ethnicity (Hispanic or Latino, not Hispanic or Latino, Not reported, Unknown)
- Race (Caucasian, African, Asian, Other)
- Smoking status (Never smokers, Former smokers, Current smokers, Unknown)
- Flu vaccination history within a year (Yes, No)

Summary tables will be presented for ITT, ITTI, and PK populations. Also data will be listed for the ITT population.

8.2 Clinical Characteristics

The following continuous variables will be summarized using descriptive statistics by treatment group:

- Duration from onset of illness to study drug administration (hours): [Start date/time of study drug administration] – [Date/time of onset of illness]
- Influenza symptoms score at screening: Average scores of respiratory, constitutional, systemic and total symptoms
- Body temperature (°C) at screening

The following categorical variables will be summarized in contingency tables:

- Influenza subtype (Influenza A/H1, Influenza A/H3, Influenza A/H1 and H3, Unknown, NA)
- Influenza confirmed (by cell culture, qPCR, both, no)
- Rapid kit test results (positive, negative)

When influenza A virus load from qPCR has quantitative value or less than Lower Limit of Quantification (LLOQ), then influenza is confirmed. However, when influenza A virus load from cell culture has only quantitative value, then influenza is confirmed by cell culture.

Summary tables will be presented for ITT, ITTI, and PK populations. Also data will be listed for the ITT population.

